Lowndes	11,147	73.7	31.4	12.2	1.5
Marengo	20,692	52.0	25.9	11.7	5.5
Perry	11,861	68.8	35.4	17.5	4.3
Pickens	19,746	43.0	27.7	14.9	5.0
Sumter	14,798	73.6	38.7	12.2	3.6
Wilcox	13,183	72.2	39.9	12.2	3.1
ALABAMA	4,802,740	26.3	19.0	11.8	20.6
US	314,918,000	12.6	15.9	8.3	25.7

2010 Census; 2008 Alabama Department of Public Health and BRFSS; PCP=Primary Care Providers per 10,000 people, from Board of Medical Examiners of Alabama and Kaiser Family Foundation.

People living with diabetes in the Black Belt have a high prevalence of medication nonadherence. Diabetic black individuals participating in the national population-based REasons for Geographic And Racial Differences in Stroke (REGARDS) epidemiology study are contrasted with those participating in the Encourage study in Table 2. Medication nonadherence as assessed by Morisky’s scale was more prevalent in the Black Belt sample, as were lower levels of education and income, demonstrating that diabetic black Americans living in the Black Belt are particularly disadvantaged. However, there is currently little understanding of the barriers to better adherence in this population, and no data on effective strategies to improve the situation.

Table 2. Black individuals with diabetes from the REGARDS (national, 2003-7) and Encourage (Alabama Black Belt, 2010) studies.

Characteristics	REGARDS	Encourage
N	3692	337
Mean Age, years±SD	65.0±8.6	58.7±12.5
Female, %	60.8	77.1
Education ≤ High School, %	53.9	75.8
Income < \$20,000, %	31.3	46.0
Insulin Use, %	31.9	40.9
Nonadherent, %	30.7	56.4

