## Recruitment of Participants

We will use respondent-driven sampling for recruitment. Flyers and interest cards are distributed by the community coordinators to their recruitment team. Flyers include the general purpose of the study and inclusion and exclusion criteria. Interested individuals sign an interest card with their contact information, which is forwarded to the research team based in Birmingham.

Prospective participants are screened for eligibility by a member of the research team over the telephone. Adults age >18 years with type 2 diabetes who respond “yes” to any question on the 4-item Morisky scale who are willing to watch a DVD and work with a peer coach to improve their diabetes self-care will be eligible for the study. Exclusion criteria include nursing home residence, plans to move away in the next year, and advanced illnesses such as hemodialysis, cancer or dementia. *The participant eligibility screening script is included in appendix D.*

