### Power Calculations and Sample Size

This study is powered to detect clinically meaningful differences in changes in medication adherence, A1c, blood pressure and LDL-cholesterol between either of the intervention arms compared with the usual care arm. The secondary outcomes are based on surveys (disease acceptance, quality of life). To consider the clustering of patients within town, we used a variance inflation factor  $D = [1 + \rho(m - 1)]$ , where  $m$  is the number of participants per community and  $\rho$  is the intra-class correlation (ICC). We conservatively estimate that we will have at least 80 clusters, corresponding to an average of 6-8 participants per cluster, with ICC=0.01 and 0.05 yielding  $D=1.084$  and  $1.419$ , respectively. Dividing the sample size per group  $N$  by  $D$  gives  $N_{\text{EFF}}$ , the effective sample size. In the Encourage study, those reporting nonadherence at baseline demonstrated ICCs in the range of 0.001-0.015 for most measures. To be conservative because we include new communities, we present power calculations for ICC=0.01-0.05. We observed 20% attrition over one year in the Encourage study and although attrition is likely to be lower over 6 months, we assume 20% attrition here, leaving 200 participants per group. Table 7 displays the detectable differences in adherence proportions and the difference in mean changes between groups detectable with 80% power using 2-sided  $X^2$  and t-tests with  $\alpha=0.05$ . We used variances based on the Encourage sample reporting nonadherence at baseline. We hypothesize that the intervention will result in improved medication adherence. Because eligibility requires low adherence at baseline, we expect low acceptance at baseline. Starting with low baseline values by design eliminates ceiling effects and allows us to reasonably anticipate large changes in the intervention groups and only modest changes in the control arm, as was seen in a storytelling intervention directed at blood pressure. For  $N=200$  per group, the difference in rates of medication adherence treated as a binary outcome detectable with 80% power depends on the proportion observed in the intervention group. If adherence is only 20% in the intervention group, then we can detect as different rates among the control group of 8.8-10.1%, depending on ICC. These rates are both lower than we anticipate for the intervention group and considerably higher than we expect in the control group. Assuming 200 participants per group we will have 80% power using 2-sided t-tests to detect differences of 0.28-0.32 standard deviations for continuous outcomes. Using variance estimates from Encourage data for change in the Diabetes Distress Score, another validated psychometric instrument, this translates into detecting differences as small as 3.7-4.4% of the range. Similarly, detectable differences for change in A1c are in a clinically meaningful range from 0.41-0.48%. We anticipate detectable differences for systolic blood pressure of 3-4 mmHg, and for LDL-cholesterol of 6.7-8.1 mg/dL.

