
### Data Analysis

The main hypothesis to be tested is that participants in the intervention group will have higher medication adherence and significantly greater improvement in A1c, blood pressure, LDL-cholesterol, and measures of quality of life; and fewer barriers to adherence compared to control patients. While medication adherence can be considered as a continuous variable, we will follow the literature and treat adherence as a binary outcome by classifying participants as non-adherent if measured adherence is <80% and adherent otherwise. Therefore, unadjusted testing of the main hypothesis will use two-sided  $X^2$  tests and statistical modeling will use logistic

regression. The other primary outcomes (A1c, blood pressure, LDL-cholesterol) and the secondary study outcomes of physical and mental functioning, as measured by the SF-12, diabetes distress, and barriers to adherence are all continuous or ordinal measures. As such unadjusted hypothesis tests for these outcomes will use t-tests or the Wilcoxon-Mann-Whitney test, as appropriate, and statistical modeling will use linear regression. Analysis will begin by calculating ICCs for each outcome to assess the magnitude of clustering; if the ICCs are found to be significantly non-zero with  $p < 0.05$  or with a point estimate greater than 0.01, testing of main hypotheses will use unadjusted regression models (logistic or linear, as appropriate) with Generalized Estimating Equations (GEE) to account for clustering. All regression models for outcomes with non-negligible ICCs will use GEE to account for clustering due to randomization at the town level, and will be repeated using mixed models treating the towns as random effects with results examined for consistency.

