The primary analysis will test the hypothesis that medication adherence treated as a binary outcome will be greater in the treatment arm than the control arm at follow-up. As above, the primary unadjusted hypothesis test will use either a  $X^2$  test or logistic regression with GEE depending on the magnitude of observed ICCs. Statistical significance will be judged by  $p < 0.05$  for either the  $X^2$  test or the coefficient for study group in regression models. The intervention group will be compared to the control group; further analyses will use logistic regression with GEE to model adjusting for any covariates that were imbalanced between groups at baseline, and will then proceed to examine regression models adjusted for the covariates described in Table 6.

Analysis for A1c, blood pressure and LDL-cholesterol and the secondary outcomes will be very similar to the analysis of medication adherence described above. We note that we will also be able to analyze adherence as a continuous outcome as a secondary analysis using the following approach. For each of these continuous or ordinal measures, we will begin by calculating the change from baseline to 6-month follow-up for each participant. These change scores will be the units of analysis and we hypothesize greater change among the intervention groups compared to the control group. We will proceed to examine summary statistics, histograms, and scatter plots of the measured outcomes for outliers and data trends. We will then test for unadjusted differences in changes between the intervention and control groups using t-tests, Mann-Whitney-Wilcoxon tests, or regression models with GEE to account for clustering, as appropriate for the variable and ICC. Similar to above, we will then proceed with more sophisticated analyses in stages, first adjusting for baseline values of outcome variables, then for any factors that were imbalanced at baseline and finally adjusting for covariates mentioned above.

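### The very low control adherence behind the primary-outcome power statement has no stated rate or source, so the claimed margin is unsupported

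*Combined protocol and SAP*

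**What the plan says.** Power Calculations and Sample Size takes 200 analysable participants per arm ("we assume 20% attrition here, leaving 200 participants per group") and allows for clustering by town, "with ICC=0.01 and 0.05 yielding $D=1.084$ and $1.419$ , respectively". For binary adherence it works one case in the text: 20% in the intervention arm, presented as a low figure, against which control rates of 8.8–10.1% can be detected with 80% power, depending on the ICC. It then says: "These rates are both lower than we anticipate for the intervention group and considerably higher than we expect in the control group". No number is attached to either expectation. The support offered is that eligibility forces low adherence at baseline, and that a storytelling trial aimed at blood pressure saw only modest change in its controls.

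Three other places bear on this:

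- Recruitment of Participants admits anyone who answers yes to "any question on the 4-item Morisky scale".
- Data Analysis defines the endpoint by "classifying participants as non-adherent if measured adherence is <80% and adherent otherwise". The main test of this endpoint is unadjusted.
- Background and Significance, Table 2, gives 56.4% non-adherent among 337 Black Encourage participants with diabetes. The text notes that nonadherence "was more prevalent in the Black Belt sample" than in the national cohort.

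**The concern.** A control rate well under 9% means that more than nine in ten controls who entered as non-adherent are still classed so six months later. The entry rule makes this doubtful. People are selected on as little as one self-reported answer, and the protocol concedes under Primary Outcomes that self-report is open to recall and social desirability bias. When the same questions are asked again, some people will change that one answer with no intervention at all. Controls also receive a Health Report Card and repeated retention calls and postcards.

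What is at stake is how the primary result is read. Between 0 and 50%, a higher control rate means a larger binomial variance, so a gap detectable at 9% is harder to detect at 20%. A reader who takes 10 to 11 points as reliably detectable could read a null result as evidence of no effect.

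**Working it through.** **Inputs from the plan.** 200 per arm after attrition; D = 1.084 (ICC 0.01) and 1.419 (ICC 0.05); two-sided 0.05; 80% power; Encourage adherence 100 − 56.4 = 43.6%. The effective sizes are 200/1.084 = 184.5 and 200/1.419 = 140.9 per arm.

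**Step 1: the plan's own figure.** For the pooled two-proportion test with n per arm and mean rate p̄,

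power = Φ{ [|p1 − p2|√n − 1.96√(2p̄(1 − p̄))] / √(p1(1 − p1) + p2(1 − p2)) }.

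For 20% v 10.1% at n = 184.5: (0.099 × 13.58 − 1.96 × 0.5057)/0.5008 = 0.706, so power is 76.0%. For 20% v 8.8% at n = 140.9 it is 76.6%. The control rates that give 80% power against 20% are 9.7% and 8.4%, so the stated 10.1% and 8.8% do not quite follow from the stated D. The plan's gaps are 20 − 10.1 = 9.9 points (low ICC) and 20 − 8.8 = 11.2 points (high ICC).

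**Step 2: what a rate below 8.8% would require.** Assume (a) Encourage classed adherence with the same cut-off, (b) the population is stable, so the adherent proportion q = 0.436 at both times, and (c) the four items are scored as a percentage, so that one yes is 75% and non-adherent, and only four no answers are adherent. With chance-corrected agreement κ between the two occasions, the probability of moving from non-adherent to adherent is q(1 − q)(1 − κ). Dividing by 1 − q gives

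P(adherent at 6 months | non-adherent at entry) = 0.436 × (1 − κ).

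Setting this to 0.088 gives κ = 1 − 0.088/0.436 = 0.80; setting it to 0.05 gives 0.89. In the other direction:

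| κ (assumed) | 0.8 | 0.7 | 0.6 | 0.5 | 0.4 |
|---|---|---|---|---|---|
| Control adherence | 8.7% | 13.1% | 17.4% | 21.8% | 26.2% |

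The documents give no κ.

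**Step 3: consequence for power at the stated D.** Example: 29.9% v 20% at n = 184.5 gives (0.099 × 13.58 − 1.96 × 0.6120)/0.6080 = 0.239, so 59%.

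| Control adherence | Power, 9.9 points, D = 1.084 | Power, 11.2 points, D = 1.419 | Gap with 80% power (D = 1.084 to 1.419) |
|---|---|---|---|
| 10% | 76% | 74% | 10.4 to 12.2 points |
| 15% | 66% | 64% | 11.8 to 13.7 points |
| 20% | 59% | 58% | 12.8 to 14.8 points |
| 25% | 55% | 53% | 13.5 to 15.6 points |

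**Step 4: larger effects.** For 20% v 35%, power is 90% (D = 1.084) and 81% (D = 1.419). For 20% v 40% it is 99% and 96%.

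**Step 5: sensitivity to D.** The stated D values imply m = 1 + 0.084/0.01 = 9.4 participants per cluster, not the 6 to 8 in the text. With m = 500/80 = 6.25, D is 1.0525 and 1.2625, and the last column becomes 10.3–11.4, 11.6–12.9, 12.6–13.9 and 13.3–14.7 points. Power at the plan's gaps is then 68/70% at 15% control adherence and 61/63% at 20%. The conclusion does not depend on the choice of D.

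**The case against.** A reader might infer that the trial lacks the power it claims. The documents do not support that. Power depends on both arms, and the intervention rate is not stated; the section treats 20% as a low case and anticipates large changes under intervention. The 9.9 and 11.2 points are the smallest gaps detectable in one worked example, not the hypothesised effect, and Step 4 shows that larger effects keep high power even over 20% control adherence.

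Nor do the documents show that control adherence will be 13–26%. The Encourage figure is a single cross-sectional one from people not selected for nonadherence. The formula in Step 2 does condition on being non-adherent at entry, which answers part of this, but the common cut-off, the stable population, the four-item scoring and κ are all assumed. A κ above 0.80 cannot be excluded.

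A reader might also infer that the plan looked at no other control rate. The section refers to a Table 7 of detectable differences in adherence proportions, which is not in the text available to me, so I do not claim this.

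What remains is narrower. The section makes a firm statement about control adherence with no rate and no source, and its own entry rule and earlier sample give reason to doubt it.

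**Conclusion.** The point holds as a gap in support. A control rate of 8.8% or less needs six-month agreement of about 0.80 or more under the three assumptions in Step 2, and the plan offers nothing to show that the scale behaves this way in this population. If control adherence is 15–20%, power for the plan's own gaps is about 66/64% to 59/58% at the stated D, against 76/77% for the plan's own worked pairs. If the true effect is 20 points over 20% control adherence, power is at least 96% and the doubt about the control rate does little harm. Which case applies cannot be settled from the documents.

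**What to change.** 1. In Power Calculations and Sample Size, replace the sentence with expected adherence in each arm and the source. An obvious candidate is follow-up adherence among Encourage participants who were non-adherent at baseline, a subset that the section already uses for its variances and ICCs. Add the detectable difference at control adherence of 10, 15, 20 and 25%: at the stated D, 10.4–12.2, 11.8–13.7, 12.8–14.8 and 13.5–15.6 points. Recompute these if D is corrected to match 6 to 8 participants per cluster.
2. In Data Analysis, make the primary logistic/GEE model for binary adherence adjust for the baseline Morisky score, and keep the unadjusted test as a supporting analysis. Everyone enters as non-adherent, but the number of yes answers can run from 1 to 4, so the score may carry information that the binary status at entry cannot. The scale is already listed under Additional Measures. The documents do not allow the gain in power to be computed, and I claim no size for it.

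The cost is wording in the protocol and SAP, with no extra participants or data. The stated detectable difference becomes less favourable, and the primary odds ratio becomes conditional on the baseline score.

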**Aim 2:** Conduct a randomized controlled trial with 500 individuals with type 2 diabetes and medication nonadherence. The trial will compare the effect of usual care and the intervention on medication adherence and physiologic risk factors including A1c, blood pressure and low density lipoprotein cholesterol (primary outcomes), and quality of life and self-efficacy (secondary outcomes).

This innovative approach would be a major shift in how we help patients in under resourced areas living with chronic diseases commit to taking medications, improving health and eventually reducing health disparities.

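### The detectable differences printed in the power section do not follow from its own sample size and design effects, and the design effects do not match its stated town size

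*Combined protocol and SAP*

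**What the plan says.** All the inputs stand in the section Power Calculations and Sample Size. Study Aims sets the total at 500 randomised. For attrition the power section says "we assume 20% attrition here, leaving 200 participants per group", which agrees with 500 × 0.8 / 2 = 200. Clustering by town enters through D = 1 + ICC × (m − 1), and the effective size per group is N/D. The section expects at least 80 towns with an average of 6-8 participants each, and prints D = 1.084 for ICC 0.01 and D = 1.419 for ICC 0.05. Tests are two-sided at 0.05. On the ICCs behind the results it says "we present power calculations for ICC=0.01-0.05".

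The results are then given in three forms:

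- Continuous outcomes: "Assuming 200 participants per group we will have 80% power using 2-sided t-tests to detect differences of 0.28-0.32 standard deviations for continuous outcomes".
- Adherence, if the intervention arm reaches 20%: "then we can detect as different rates among the control group of 8.8-10.1%, depending on ICC".
- Individual outcomes in their own units, for example "and for LDL-cholesterol of 6.7-8.1 mg/dL".

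The section cites a Table 7 for these figures. That table is not in the text available to us, so the check below is of the prose.

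**The concern.** The section gives N, D, alpha, power and the test, so the SD and adherence figures can be recomputed without any outside input. They do not come out as printed. All four printed figures are more favourable than the printed D allows, by a similar amount, so rounding or a different choice of test is an unlikely explanation. These figures justify the size of a town-randomised trial, and the adherence figure concerns the outcome that Data Analysis names for the primary test. If they are too favourable, the stated 80% power is not what the plan's own assumptions deliver.

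**Working it through.** **Inputs** (all from Power Calculations and Sample Size): N = 200 per group; D = 1.084 and 1.419; two-sided alpha 0.05 (z = 1.960); power 80% (z = 0.8416); m = 6-8; ICC 0.01 and 0.05.

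**Formulas.** Effective size n = N/D. Detectable difference in SD units = (1.960 + 0.8416) × √(2/n). For adherence, the pooled two-proportion chi-square power formula with 20% in the intervention arm, solved for the control rate that gives 80% power.

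**Step 1: the printed D.**

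- D = 1.084: n = 200/1.084 = 184.5; difference = 2.8016 × √(2/184.5) = 0.292 SD; control rate 9.7%.
- D = 1.419: n = 200/1.419 = 140.9; difference = 2.8016 × √(2/140.9) = 0.334 SD; control rate 8.4%.

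The exact t-test gives 0.293 and 0.335 SD. The arcsine method gives control rates of 9.8% and 8.6%. Neither recovers the printed 0.28-0.32 SD or 10.1% and 8.8%.

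**Step 2: power at the printed differences with the printed D.**

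| Printed difference | D | Power |
|---|---|---|
| 0.28 SD | 1.084 | 76.7% (t: 76.5%) |
| 0.32 SD | 1.419 | 76.6% (t: 76.3%) |
| 20% vs 10.1% | 1.084 | 76.0% |
| 20% vs 8.8% | 1.419 | 76.7% |

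At the upper rounding limits, 0.285 and 0.325 SD, power is still about 78%.

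**Step 3: is the printed D consistent with m?** Solving D = 1 + ICC × (m − 1) for m gives 0.084/0.01 + 1 = 9.4 and 0.419/0.05 + 1 = 9.38. The text says 6-8, and 500/80 = 6.25. So the printed D is itself at odds with the stated town size.

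**Step 4: the same calculation with the stated m and N = 200.**

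| ICC | m | D | Detectable SD | Control rate vs 20% | Power at the printed differences |
|---|---|---|---|---|---|
| 0.01 | 6 | 1.05 | 0.287 | 9.8% | 78.0% (0.28 SD); 77.3% (10.1%) |
| 0.01 | 8 | 1.07 | 0.290 | 9.7% | 77.2% (0.28 SD); 76.5% (10.1%) |
| 0.05 | 6 | 1.25 | 0.313 | 9.0% | 81.7% (0.32 SD); 81.7% (8.8%) |
| 0.05 | 7 | 1.30 | 0.319 | 8.8% | 80.1% (0.32 SD); 80.2% (8.8%) |
| 0.05 | 8 | 1.35 | 0.326 | 8.6% | 78.6% (0.32 SD); 78.7% (8.8%) |

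The unfavourable ends come back at m of about 7. The favourable ends do not come back at any stated m.

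**Step 5: what would reproduce the printed figures?**

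- No clustering (D = 1, N = 200): 0.280 SD; control rate 10.0% by chi-square or 10.1% by arcsine. This fits the favourable ends only.
- The printed D with a larger N: 217 per group gives 0.280 and 0.320 SD, 10.0% and 8.8%; 219 per group gives 0.279 and 0.319 SD, 10.1% and 8.8%. This fits all four, but 217-219 is not a number in the plan.

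**Step 6: a check that needs no SD.** Both ends of any one outcome's range share the same SD and N, so upper/lower = √(D at ICC 0.05 / D at ICC 0.01). The printed D gives √(1.419/1.084) = 1.144; m = 6-8 gives 1.09-1.12. Allowing for rounding, the SD range permits a ratio of at most 0.325/0.275 = 1.182, while LDL requires at least 8.05/6.75 = 1.193. No single pair of D values serves both.

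**The case against.** Four points can be made for the plan.

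- **The 76-77% rests on D values that the section itself contradicts.** This stands. With m = 6-8, power at 0.32 SD is about 79-82%, and the unfavourable ends are sound at m of about 7. It does not rescue 0.28 SD or 10.1%.
- **A reader might infer that clustering was left out of the favourable ends.** They do lie close to an unclustered result, but the documents do not support that as the cause. Under the stated chi-square test, D = 1 gives 10.0%, not 10.1%. The printed D with 217-219 per group fits the figures at least as well, and the ratio 0.32/0.28 = 1.143 is what one would see had both printed D values been applied. Either explanation is inference.
- **The effect on the trial is small.** This also stands. The 20% rate is illustrative, and the section expects a higher rate in the intervention arm and a considerably lower one in the control arm, so 76% is not the power for the effect the investigators anticipate. The section calls its ICC range conservative (Encourage: 0.001-0.015 for most measures) and expects attrition below 20%.
- **Table 7 may hold correct figures.** It may, but the paragraph still needs to agree with its own inputs.

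A reader might also want replacement LDL values. They cannot be derived: the Encourage SD for LDL is not given and the right D is in dispute. Only the mismatch in ratio can be shown, and its margin is narrow (1.193 against 1.182).

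**Conclusion.** The paragraph is wrong as written, to a modest degree. Taking N = 200 and the printed D as given, the 80%-power differences are 0.29-0.33 SD and control rates of 9.7% and 8.4%; the printed differences carry about 76-77% power. Taking N = 200 and the stated m = 6-8 instead, the range is about 0.287 to 0.326 SD and about 9.8% to 8.6%; power is 77-78% at 0.28 SD and about 79-82% at 0.32 SD. The conclusion common to both readings is that 0.28 SD and 10.1% are not attainable with 80% power at ICC 0.01. Separately, the printed D and the stated town size cannot both be right, and the LDL range cannot share one pair of D values with the SD range. The A1c, distress and systolic blood pressure figures cannot be recomputed from the documents. The finding does not show that clustering was ignored, nor that the trial is underpowered for the effect it expects.

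**What to change.** Settle m, D and N first, then restate every figure in the paragraph, and Table 7 if it is affected, from that one set:

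- If the printed D is kept, correct the stated town size to match, and give 0.29-0.33 SD and control rates of 9.7% and 8.4% against 20%.
- If m = 6-8 is kept, replace D by 1.05-1.07 and 1.25-1.35, and give about 0.29 SD at ICC 0.01 and 0.31-0.33 SD at ICC 0.05, with control rates of about 9.7-9.8% and 8.6-9.0%.

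Recompute A1c, distress, systolic blood pressure and LDL from the Encourage SDs with the same D values, and state those SDs so that the figures can be checked. Alternatively, keep the printed differences and state the lower power that results. If N was meant to be something other than 200, say so and show where it comes from.

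The cost is one rewritten paragraph with slightly less favourable numbers. Enrolment, conduct and analysis do not change.
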